### **5.3.5.9 Hospitalization or Prolonged Hospitalization**

Any adverse event that results in hospitalization or prolonged hospitalization should be documented and reported as a serious adverse event (per the definition of serious adverse event in Section 5.2.2), except as outlined below.

The following hospitalization scenarios are not considered to be serious adverse events:

- Hospitalization for respite care
- Hospitalization for a preexisting condition, provided that all of the following criteria are met:
  - The hospitalization was planned prior to the study or was scheduled during the study when elective procedure became necessary because of the expected normal progression of the disease
  - The patient has not suffered an adverse event
- Hospitalization due solely to recurrence/progression of the underlying melanoma

### **5.3.5.10 *Adverse Events Associated with an Overdose or Error in Drug Administration***

Study drug overdose is the accidental or intentional use of the drug in an amount higher than the dose being studied. An overdose or incorrect administration of study drug is not an adverse event unless it results in untoward medical effects. Any study drug overdose or incorrect administration of study drug should be noted on the Study Drug Administration eCRF.

All adverse events associated with an overdose or incorrect administration of study drug should be recorded on the Adverse Event eCRF. If the associated adverse event fulfills serious criteria, the event should be reported to the Sponsor within 24 hours after learning of the event (see Section 5.4.2).

### **5.3.5.11 Patient-Reported Outcome Data**

Adverse event reports will not be derived from PRO data, *and safety analyses will not be performed using PRO data*. However, if any patient responses suggestive of a possible adverse event are identified during site review of the PRO questionnaires, site staff will alert the investigator, who will determine if the criteria for an adverse event have been met and will document the outcome of this assessment in the patient's medical record per site practice. If the event meets the criteria for an adverse event, it will be documented in the patient's source document and reported on the Adverse Event eCRF.

## **5.4 IMMEDIATE REPORTING REQUIREMENTS FROM INVESTIGATOR TO SPONSOR**

Certain events require immediate reporting to allow the Sponsor to take appropriate measures to address potential new risks in a clinical trial. The investigator must report such events to the Sponsor immediately; under no circumstances should reporting take place more than 24 hours after the investigator learns of the event. The following is a list of events that the investigator must report to the Sponsor within 24 hours after learning of the event, regardless of relationship to study drug:

- Serious adverse events
- Adverse events of special interest
- Pregnancies

The investigator must report new significant follow-up information for these events to the Sponsor immediately (i.e., no more than 24 hours after becoming aware of the information). New significant information includes the following:

- New signs or symptoms or a change in the diagnosis
- Significant new diagnostic test results
- Change in causality based on new information
- Change in the event's outcome, including recovery
- Additional narrative information on the clinical course of the event

Investigators must also comply with local requirements for reporting serious adverse events to the local health authority and IRB/EC.

### **5.4.1 Emergency Medical Contacts**

#### **Medical Monitor Contact Information**

**24 HOUR MEDICAL COVERAGE (Roche Emergency Medical Call Center Help Desk):** To reach the Roche Emergency Medical Call Center Help Desk please refer to your Regulatory binder for country-specific access numbers.

To ensure the safety of study patients, an Emergency Medical Call Center Help Desk will access the Roche Medical Emergency List, escalate emergency medical calls, provide

medical translation service (if necessary), connect the investigator with a Roche Medical Monitor, and track all calls. The Emergency Medical Call Center Help Desk will be available 24 hours per day, 7 days per week. Toll-free numbers for the Help Desk and Medical Monitor contact information will be distributed to all investigators (see "Protocol Administrative and Contact Information and List of Investigators").

#### **5.4.2 Reporting Requirements for Serious Adverse Events and Adverse Events of Special Interest**

For reports of serious adverse events and adverse events of special interest, investigators should record all case details that can be gathered immediately (i.e., within 24 hours) on the Adverse Event eCRF and submit the report via the electronic data capture (EDC) system. A report will be generated and sent to Roche Safety Risk Management by the EDC system.

In the event that the EDC system is unavailable, a paper Serious Adverse Event/ Adverse Event of Special Interest CRF and Fax Coversheet should be completed and faxed to Roche Safety Risk Management or its designee immediately (i.e., no more than 24 hours after learning of the event), using the fax numbers provided to investigators (see "Protocol Administrative and Contact Information & List of Investigators"). Once the EDC system is available, all information will need to be entered and submitted via the EDC system.

#### **5.4.3 Reporting Requirements for Pregnancies**

##### **5.4.3.1 Pregnancies in Female Patients**

Female patients of childbearing potential will be instructed to immediately inform the investigator if they become pregnant during study treatment or within 6 months after the last dose of study drug. All women of childbearing potential will have a serum pregnancy test at screening.

A Pregnancy Report eCRF should be completed by the investigator immediately (i.e., no more than 24 hours after learning of the pregnancy) and submitted via the EDC system. A pregnancy report will automatically be generated and sent to Roche Safety Risk Management. Pregnancy should not be recorded on the Adverse Event eCRF. The investigator should discontinue study drug and counsel the patient, discussing the risks of the pregnancy and the possible effects on the fetus. Monitoring of the patient should continue until conclusion of the pregnancy.

In the event that the EDC system is unavailable, a Pregnancy Report worksheet and Pregnancy Fax Coversheet should be completed and faxed to Roche Safety Risk Management or its designee within 24 hours after learning of the pregnancy, using the fax numbers provided to investigators (see "Protocol Administrative and Contact Information and List of Investigators").

### **5.4.3.2 Pregnancies in Female Partners of Male Patients**

Male patients will be instructed through the Informed Consent Form to immediately inform the investigator if their partner becomes pregnant during study treatment or within 6 months after the last dose of study drug.

A Pregnancy Report eCRF should be completed by the investigator immediately (i.e., no more than 24 hours after learning of the pregnancy) and submitted via the EDC system. Attempts should be made to collect and report details of the course and outcome of any pregnancy in the partner of a male patient exposed to study drug. The pregnant partner will need to sign an Authorization for Use and Disclosure of Pregnancy Health Information to allow for follow-up on her pregnancy. Once the authorization has been signed, the investigator will update the Pregnancy Report eCRF with additional information on the course and outcome of the pregnancy.

An investigator who is contacted by the male patient or his pregnant partner may provide information on the risks of the pregnancy and the possible effects on the fetus, to support an informed decision in cooperation with the treating physician and/or obstetrician.

In the event that the EDC system is unavailable, follow reporting instructions provided in Section [5.4.3.1](#).

### **5.4.3.3 Abortions**

Any abortion associated with a pregnancy occurring during the study or within 6 months of the last dose of study drug should be classified as a serious adverse event (as the Sponsor considers abortions to be medically significant events), recorded on the Adverse Event eCRF, and reported to the Sponsor immediately (i.e., no more than 24 hours after learning of the event; see Section [5.4.2](#)).

### **5.4.3.4 Congenital Anomalies/Birth Defects**

Any congenital anomaly/birth defect in a child born to a female patient or female partner of a male patient exposed to study drug during the study or within 6 months of the last dose of study drug should be classified as a serious adverse event, recorded on the Adverse Event eCRF, and reported to the Sponsor immediately (i.e., no more than 24 hours after learning of the event; see Section [5.4.2](#)).

#### **5.4.4 New Non-Cutaneous Primary Cancers**

In fulfillment of a post-marketing requirement as a condition of vemurafenib approval in the United States (for the treatment of locally-advanced Stage IIIC or metastatic melanoma), all non-melanoma, new non-cutaneous primary cancers will be reported to the U.S. FDA every 12 months after the first patient enrolls and for 12 months after the last patient has completed study treatment.

### **5.5 FOLLOW UP OF PATIENTS AFTER ADVERSE EVENTS**

#### **5.5.1 Investigator Follow Up**

The investigator should follow each adverse event until the event has resolved to baseline grade or better, the event is assessed as stable by the investigator, the patient is lost to follow up, or the patient withdraws consent. Every effort should be made to follow all serious adverse events considered to be related to study drug or trial-related procedures until a final outcome can be reported.

During the study period, resolution of adverse events (with dates) should be documented on the Adverse Event eCRF and in the patient's medical record to facilitate source data verification. If, after follow-up, return to baseline status or stabilization cannot be established, an explanation should be recorded on the Adverse Event eCRF.

All pregnancies reported during the study should be followed until pregnancy outcome. If the EDC system is not available at the time of pregnancy outcome, follow reporting instructions provided in Section 5.4.3.1.

#### **5.5.2 Sponsor Follow Up**

For serious adverse events, adverse events of special interest, and pregnancies, the Sponsor or a designee may follow up by telephone, fax, electronic mail, and/or a monitoring visit to obtain additional case details and outcome information (e.g., from hospital discharge summaries, consultant reports, autopsy reports) in order to perform an independent medical assessment of the reported case.

### **5.6 POST-STUDY TREATMENT ADVERSE EVENTS**

At the end-of-study-treatment visit and at the 4-week after end-of-study-treatment visit, the investigator should instruct each patient to report to the investigator any subsequent adverse events that the patient's personal physician believes could be related to prior study drug treatment or study procedures.

The investigator should notify the Sponsor of any death, serious adverse event (including new primary malignancies), or other adverse event of *special interest* occurring at any time after a patient has discontinued study participation if the event is believed to be related to prior study drug treatment or study procedures. The Sponsor should also be notified if the investigator becomes aware of the development of cancer or a congenital anomaly/birth defect in a subsequently conceived offspring of a patient that participated in this study.

The investigator should report these events to Roche Safety Risk Management on the Adverse Event eCRF. If the Adverse Event eCRF is no longer available, the investigator should report the event directly to Roche Safety Risk Management via telephone (see "Protocol Administrative and Contact Information and List of Investigators").

During survival follow-up, deaths attributed to progression of melanoma should be recorded only on the Survival eCRF.

## **5.7 EXPEDITED REPORTING TO HEALTH AUTHORITIES, INVESTIGATORS, INSTITUTIONAL REVIEW BOARDS, AND ETHICS COMMITTEES**

The Sponsor will promptly evaluate all serious adverse events and adverse events of special interest against the cumulative product experience to identify and expeditiously communicate possible new safety findings to investigators, IRBs, ECs, and applicable health authorities based on applicable legislation.

To determine reporting requirements for single adverse event cases, the Sponsor will assess the expectedness of these events using the following reference documents:

- Cobimetinib IB
- Vemurafenib IB

The Sponsor will compare the severity of each event and the cumulative event frequency reported for the study with the severity and frequency reported in the applicable reference document.

Reporting requirements will also be based on the investigator's assessment of causality and seriousness, with allowance for upgrading by the Sponsor as needed.

## **6. STATISTICAL CONSIDERATIONS AND ANALYSIS PLAN**

### **6.1 DETERMINATION OF SAMPLE SIZE**

#### **6.1.1 Progression-Free Survival**

The type 1 error ( $\alpha$ ) for the analysis of the primary endpoint of PFS is 0.05 (2-sided).

Approximately 500 patients will be randomized to treatment. The final analysis of the primary endpoint of PFS will take place when approximately 206 PFS events have occurred. Statistical considerations are based on the following assumptions:

- Stratified log-rank test at 0.05 significance level (2-sided)
- 6 months median PFS for the vemurafenib + placebo arm
- 11 months median PFS for the vemurafenib + cobimetinib arm
- Accrual ramp-up time of 9 months to reach 65 patients per month thereafter for a total enrollment period of approximate 14 months
- 5% dropout rate

- No interim analysis of PFS

A total of 206 PFS events provides >95% power to detect an improvement in median PFS from 6 months in the vemurafenib + placebo arm to 11 months in the vemurafenib + cobimetinib arm (corresponding to a hazard ratio of 0.55, and the minimal detectable difference [MDD] is 0.76).

### **6.1.2 Overall Survival**

See Section 6.9.2 for a description of the planned interim analysis and final analysis of OS. The type 1 error ( $\alpha$ ) for the analysis of the secondary endpoint of OS is 0.05 (2-sided).

The final analysis of OS will be performed after the occurrence of approximately 250 deaths. A total of 250 deaths provides approximately 80% power to detect an improvement in median OS from 15 months in the vemurafenib + placebo arm to 21.4 months in the vemurafenib + cobimetinib arm (corresponding to a hazard ratio for death of 0.70) at an overall 2-sided 0.05 significance level.

## **6.2 SUMMARIES OF CONDUCT OF STUDY**

Enrollment, eligibility violations, and patient disposition will be summarized for randomized patients by treatment arm. Study treatment administration will be summarized by treatment arm for all treated patients.

## **6.3 SUMMARIES OF TREATMENT GROUP COMPARABILITY**

Demographic variables, stratification factors, and other baseline and disease characteristics (including disease stage and LDH) will be summarized.

## **6.4 EFFICACY ANALYSES**

Unless otherwise noted, all efficacy analyses will include all randomized patients (intent-to-treat analysis), and patients will be grouped according to the treatment assigned at randomization.

### **6.4.1 Primary Efficacy Analysis**

The primary analysis will be a comparison of PFS between the 2 treatment arms using a stratified log-rank test at an overall 0.05 significance level (2-sided).

The statistical hypothesis of this study is as follows:

$$H_0: \text{PFS}_{(\text{Arm A})} = \text{PFS}_{(\text{Arm B})}$$

$$H_1: \text{PFS}_{(\text{Arm A})} \neq \text{PFS}_{(\text{Arm B})}$$

where  $PFS_{(Arm A)}$  represents the survival function of PFS in the vemurafenib + placebo arm and  $PFS_{(Arm B)}$  represents the survival function of PFS in the vemurafenib + cobimetinib arm.

PFS as assessed by Investigator will be the primary endpoint evaluated. PFS is defined as the time between date of randomization and the date of first documented disease progression or death, whichever occurs first. Disease progression will be determined based on investigator assessment using RECIST v1.1. Data from patients who have not experienced disease progression or death will be censored at the last tumor assessment date. Data from patients with no post-baseline tumor assessment will be censored at the randomization date. The hazard ratio for PFS will be estimated using a stratified Cox model. Two-sided 95% CIs for the hazard ratio will be provided. The stratified analyses will incorporate 2 stratification factors: geographic region (North America, Europe, Australia/New Zealand/others) and metastatic classification (unresectable Stage IIIc, M1a, and M1b; M1c). Results from an unstratified log-rank test and the unstratified hazard ratio will also be presented. Kaplan-Meier methodology will be used to estimate median PFS for each treatment arm, and the Kaplan-Meier curves will be provided.

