**Figure 5 Study GO28141 Dosing Scheme**

BID = twice daily; D = day; QD = once daily.

All patients will be closely monitored for safety and tolerability during all cycles of therapy, at the end-of-study treatment visit, and during the follow-up period. Patients will be assessed for adverse events every 2 weeks during the first 2 cycles, then prior to each subsequent cycle, and as necessary throughout the study.

Tumor response will be evaluated according to RECIST v1.1. Any evaluable and measurable disease must be documented at screening and re-assessed at each subsequent tumor evaluation. Response will be assessed by the investigator at 8-week intervals. At the investigator's discretion, CT/MRI scans may be repeated at any time if PD is suspected.

The NCI Common Terminology Criteria for Adverse Events (CTCAE) v4.0 will be used to characterize the toxicity profile of the study treatments on all patients. ECG monitoring for patients who receive vemurafenib will be conducted in accordance with the vemurafenib IB. Ongoing ECG monitoring is no longer required for patients who continue to receive only cobimetinib/placebo unless clinically indicated. Dermatologic assessment will be performed at the beginning of Cycle 2 ( $\pm 1$  week) and per local

standard of care thereafter. Ophthalmologic examinations and left ventricular function evaluation (echocardiogram or MUGA) are evaluated throughout the study.

Treatment will continue until disease progression, death, unacceptable toxicity, or withdrawal of consent, whichever occurs earliest. Patients on the vemurafenib and placebo treatment arm will be eligible to cross over to the vemurafenib and cobimetinib treatment arm prior to disease progression so long as the patient has not discontinued vemurafenib treatment should the investigator feel that the addition of cobimetinib may benefit the patient and the patient provides informed consent and continues to be followed for survival. Patients who have previously discontinued vemurafenib and who are receiving only placebo may not cross over and should discontinue all study treatment.

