### **3.4 OUTCOME MEASURES**

#### **3.4.1 Efficacy Outcome Measures**

##### **3.4.1.1 Primary Efficacy Outcome Measure**

The primary outcome measure for this study is as follows:

- PFS, defined as the time from randomization to the first occurrence of disease progression, as determined by the investigator using RECIST v1.1 ([Appendix 3](#)), or death from any cause, whichever comes first.

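### The no-scan censoring rule for primary PFS is not limited to event-free patients, so read literally it conflicts with counting death from any cause

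*Protocol*

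**What the plan says.** Section 6.4.1 defines the primary endpoint: "PFS is defined as the time between date of randomization and the date of first documented disease progression or death, whichever occurs first". Section 3.4.1.1 gives the same definition, ending "or death from any cause, whichever comes first". Section 6.4 places all randomized patients in the efficacy analyses by assigned arm.

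Two censoring sentences follow the definition in 6.4.1. The first has a condition: "Data from patients who have not experienced disease progression or death will be censored at the last tumor assessment date". The second has none: "Data from patients with no post-baseline tumor assessment will be censored at the randomization date". The synopsis (Statistical Methods, Primary Analysis) repeats both.

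On scan timing, Section 3.1 says "Response will be assessed by the investigator at 8-week intervals" and adds that "CT/MRI scans may be repeated at any time if PD is suspected". Section 4.5.1.5 later moves scan frequency to local practice. The 8-week schedule is taken here as the one behind the primary PFS analysis.

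**The concern.** A patient who dies before any post-baseline tumor assessment fits two rules with different results. Under the endpoint definition the patient has an event on the date of death. Under the unqualified second censoring sentence the patient is censored at time zero and contributes nothing. The protocol does not say which rule governs.

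With a first scheduled scan at 8 weeks, the case can occur. These deaths are the worst outcomes in the trial. Dropping them would lengthen PFS in any arm where they happen. If they were more frequent on the combination, dropping them would hide the early harm that including death in PFS is meant to show.

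**Working it through.** **1. The plan's own figures (Section 6.1.1).** Inputs: 206 events, HR 0.55, two-sided 0.05, 1:1 allocation. Schoenfeld power = Φ(√206/2 × |ln 0.55| − 1.96) = Φ(7.176 × 0.598 − 1.96) = Φ(2.33) = 0.990. Smallest detectable effect: exp(−1.96 × 2/√206) = 0.761. Both stated values (power above 95%, 0.76) reproduce.

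**2. Upper bound on deaths before the first scan.** The documents give no rate. Assume constant hazards at the design OS medians in Section 6.1.2 (15 and 21.4 months). 8 weeks = 56/30.4375 = 1.84 months.
- Control: 1 − exp(−ln 2 × 1.84/15) = 8.15%, or 20.4 of 250.
- Combination: 1 − exp(−ln 2 × 1.84/21.4) = 5.79%, or 14.5 of 250.
- Total 34.8, which is 16.9% of 206.
- At a quarter of those hazards: 5.3 + 3.7 = 9.0, or 4.3% of 206.

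**3. Why the bound is too high.** Entry requires a life expectancy of at least 12 weeks and ECOG 0 or 1, and excludes active CNS lesions (Sections 4.1.1 and 4.1.2). Unscheduled scans take some early deaths outside the rule even when it is read literally. Table 12 reports 85 actual deaths at the OS interim, about 16 months after first patient in. The design hazards applied to 248 control and 247 combination patients, with accrual rising linearly for 9 months and then flat, and no dropout, predict about 117 deaths (14 months' enrollment) to 128 (12.7 months). The ratio 85/128 to 85/117 is 0.66 to 0.73. Applied roughly to 34.8, it leaves 23 to 25 deaths, before allowing for the entry criteria or unscheduled scans.

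**4. Power if such deaths were lost (HR 0.55).**

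| Assumed unscanned deaths, control/combination | Events lost | Power | Detectable HR |
|---|---|---|---|
| 1%/1% | 5 | 0.989 | 0.758 |
| 2%/2% | 10 | 0.987 | 0.756 |
| 5%/3% or 3%/5% | 20 | 0.983 | 0.750 |
| Upper bound | 34.8 | 0.974 | 0.741 |

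**5. Effect on the hazard ratio.** Each scenario used 3,000 simulated trials: 250 per arm, exponential PFS with control median 6 months, entry uniform over 14 months, and cutoff at the 206th event with deaths counted. The assumed fraction of patients dies unscanned between 0.2 and 1.84 months. The HR comes from the unstratified log-rank statistic, exp((O − E)/V). The HR in the first column applies to patients without an early death.

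| HR; unscanned deaths, control/combination | Deaths counted | Deaths censored at day 0 |
|---|---|---|
| 0.55; 2%/2% | 0.565 | 0.551 |
| 0.55; 5%/3% | 0.554 | 0.549 |
| 0.55; 3%/5% | 0.601 | 0.549 |
| 1.00; 2%/5% | 1.055 | 1.001 |

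With deaths censored, the estimate returns to the HR among the remaining patients, whatever happened early. The two readings separate materially only when early deaths are more frequent on the combination.

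**The case against.** The best defense is that the second sentence completes the first. The first sends event-free patients to their last assessment date, and the second supplies a date when there is none. A death is already an event, so such a patient never reaches a censoring rule. This is the natural reading, it agrees with Sections 3.4.1.1 and 6.4, and it is probably what was meant. It stands as a statement of likely intent, but the protocol does not state it.

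The OS rule in Section 6.4.2 has the same two-sentence form. That parallel shows a drafting habit but does not settle the PFS case. A death is itself survival information, so the OS fallback cannot catch a patient who died. A death is not a tumor assessment, so the PFS fallback can.

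Two further points stand. The SAP, which was not available for this review, may specify the derivation. And the primary PFS analysis is complete (Section 1.4.4: cutoff 9 May 2014, HR 0.51, 95% CI 0.39 to 0.68), so rewording cannot change it.

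A reader might infer that the plan does remove early deaths, that about 17% of events were at risk, or that the reported HR is biased. The documents support none of these. They do not show how the rule was applied, how many patients died unscanned, or in which arm. Nor is an excess of early control-arm deaths a reason for alarm: at an assumed 5%/3%, the HR moves only from 0.554 to 0.549.

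**Conclusion.** The point holds as a defect of wording in the primary analysis rule. One sentence, given twice, conflicts with the endpoint definition if followed literally, and nothing in the protocol resolves the conflict. Power is not at issue: it stays above 95% across the assumed range, including the upper bound of about 35 deaths. The number actually affected is not documented. Given the entry criteria, unscheduled scans and the interim death count, a few percent of events or less is a reasonable judgment, but it is not a derived figure.

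What matters is possible bias in one direction. An excess of unscanned early deaths on the combination would be masked, with an HR of about 0.60 counted against 0.55 censored at an assumed 3% control and 5% combination. All early-death rates here are assumptions, and whether any masking occurred cannot be told from the protocol.

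**What to change.** In Section 6.4.1 and the synopsis, replace the second censoring sentence with wording such as: *A patient with neither progression nor death and with no tumor assessment after baseline is censored on the day of randomization; a patient who dies without such an assessment has a PFS event on the date of death.* The condition should name progression as well as death, so that no documented progression is censored either.

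Then confirm that the PFS derivation used for the completed primary analysis counted deaths without a post-baseline assessment as events, and report how many there were in each arm.

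The cost is one sentence in two places and a check of one derivation. The planned 206 events, the power of 0.990 and the detectable HR of 0.76 are unchanged.
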